## 4.0 Protocol Design

#### 4.1 Study Design Overview

This multi-site, open-label study assesses the safety and effectiveness of MDMA-assisted psychotherapy in participants diagnosed with at least severe PTSD. This study will also serve as an experiential training opportunity for therapy teams who will be participating in the upcoming Phase 3 study. The sponsor will provide clinical supervision through the adherence raters and the therapy pair supervisors, who will review the therapy session videos to ensure adherence to the therapeutic method, consistency between sites and therapy pairs, and provide support and advice to the therapy pair.

The study will be conducted in up to 40 participants in multiple countries in Europe. Some sites will participate in the imaging sub-study (see Appendix A for additional details). This study will be conducted in compliance with the protocol, GCP and applicable regulatory requirement(s). All data will be included in the sponsor's safety database.

For each participant, the study will consist of:

- Screening Period: phone screen, informed consent, eligibility assessment, and enrollment of eligible participants
- Preparatory Period with Enrollment Confirmation: medication tapering, Preparatory Sessions and Baseline assessments leading to Enrollment Confirmation
- Treatment Period: two Experimental Sessions spaced a month apart and associated Integrative Sessions over ~8 weeks plus one CAPS-5 assessment
- Follow-up Period and Study Termination: ~4 weeks with no study visits, followed by Primary Outcome CAPS-5 and Study Termination visit

The treatment consists of a flexible dose of MDMA, followed by a supplemental half-dose unless tolerability issues emerge with the first dose or the participant declines, administered with manualized psychotherapy in two open-label Experimental Sessions spaced a month apart. This ~8-week Treatment Period is preceded by three Preparatory Sessions. During the Treatment Period, each Experimental Session is followed by three Integrative Sessions of non-drug psychotherapy. Experimental Sessions are followed by an overnight stay. Study design overview is shown in Table 1 and Figure 1.

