## 4.3.4 Early Termination from the Study

Participants who are removed from the study after they are enrolled and receive IP but do not complete the study may fall into one of these categories: Post-Dosing Early Termination or Dropout. If the participant has received IP in at least one Experimental Session and completed one CAPS-5 assessment beyond Baseline, they will be considered evaluable. All participants who receive IP in at least one Experimental Session will be included in all safety analyses.

Participants can withdraw from treatment or withdraw consent at any time for any reason without judgment. The site team can withdraw a participant if, in their clinical judgment, it is in the best interest of the participant or if the participant cannot comply with elements of the protocol that are critical for safety or for the scientific integrity of the study. If the site team makes the decision to terminate the participant from treatment or the study, they will explain the reason for withdrawal and document in the participant's source records and eCRF. If a participant develops any Exclusion Criteria that, in the opinion of the Medical Monitor or Site, affects the safety of the participant, including psychiatric diagnosis, pregnancy, or requiring use of prohibited medications, the participant will discontinue treatment in Experimental Sessions but remain in the study for the associated Integrative Sessions. Any time a participant terminates from the study early, the site team will attempt to obtain information about AE outcomes if appropriate, as determined by the site physician and Medical Monitor. The site team will provide the participant with an Exit Plan as described in Section 7.4.4 Exit Plan.

- Post-Dosing Early Termination: Participants who discontinue study treatment but continue to participate in study evaluations and outcome assessments. Data collection by Irs will continue on the same schedule as planned through Study Termination visit procedures.

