# 7.1.3 Interruptions and Arrangements Due to COVID-19 Pandemic or Any Other Unforeseen Emergency at Clinic Locations

This clinical trial may be impacted by the Coronavirus Disease 2019 (COVID-19) global pandemic. Special arrangements may be required for study continuation and participant and study site staff safety due to this emergency or any other unforeseen emergency in the future. The following accommodations in the protocol will be allowed, captured, and noted in the Clinical Study Report as COVID-19 deviations when applicable:

• Integrative Sessions may be conducted by tele-medicine

- Delaying the start of medication tapering after enrollment and the subsequent Treatment Period per Section 11.1 Tapering Instructions
- Delaying Experimental Sessions and associated Integrative Sessions
- Delaying Independent Rater assessments for participants who cannot complete them remotely off-site
- Use of prohibited medications and/or cannabis or initiation of new therapy for participants with significant study delays, which will be reviewed by the study team before each Experimental Session and re-tapered prior to resuming treatment per Section 11.0 Concomitant Medications.

For any participant with COVID-19 related illness, continued trial participation after full recovery of the disease may be appropriate after discussion between the site physicians and Medical Monitors on a case-by-case basis.

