#### **8.4 Bias Minimization**

Before a participant is deemed eligible and enrolled into the study, participant's medical history and screening assessments will be reviewed by the Principal Investigator and therapy team. If needed, Medical Monitor will be consulted.

Two different processes exist to ensure bias minimization: the primary and secondary outcome assessments performed by the IR team will be recorded and then reviewed by a senior (local) IR, and all psychotherapy study visits (including the experimental sessions) will be reviewed by adherence raters to ensure adherence to the Treatment Manual, and consistency among therapy pairs and sites. The paragraphs below describe these processed in more detail.

To minimize bias in measuring effect, the sponsor will use an observer-blind, centralized, reliable IR pool to administer the Primary Outcome measure via live video interviews. The IR Pool will have no knowledge of participant's study data or AEs and will only evaluate participants at Baseline and at the assessments scheduled after each Experimental Session. The IR Pool is blinded to study design, visit number, number of treatments, and any data from the treating therapy team after Baseline. IRs will be assigned to participants based on availability. Data will be entered into a dedicated IR Database by the IR Coordinator who is not part of the study assessments or procedures. Timing of CAPS-5 assessments are provided in Table 2.

To ensure that all participants are treated in a similar manner, the sites will be required to follow the protocol and Treatment Manual delineating minimum length of time per visit type and describing delivery of treatment. All Experimental Sessions are required to be at least 8 hours long. Adherence to the Treatment Manual will be checked by review of video by adherence raters. The sponsor will monitor data in real-time to ensure complete data collection for all participants, including those who discontinue treatment. Sites will be required to make and document a specific number of attempts to obtain follow-up data per protocol. All participants who receive at least one dose of IP and complete at least one follow-up assessment will be included in the final mITT analysis.

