If the participant is severely agitated, anxious, in danger of self-harm or suicide, or is experiencing any other severe psychological distress, at the end of a psychotherapy session, at least one member of the therapy team will remain with the participant for at least 2 more hours. During this time, the therapy team will employ affect management techniques, will talk with the participant to help them gain cognitive perspective of their experiences, and will help the participant implement the self-soothing and stress inoculation techniques presented during the Preparatory Sessions. If the participant remains severely anxious, agitated, in danger of self-harm

or suicide, or is otherwise psychologically unstable at the end of the 2-hour stabilization period, the site physician and therapy team will decide between the following options:

- 1. If severe distress occurs at the end of an Experimental Session, a nurse, therapeutic assistant, physician, or therapy team member should stay with the participant until the severe distress resolves or until the time of their Integrative Session appointment the following morning. The therapy team should then meet with the participant daily until the period of destabilization has passed.
- 2. If the participant experiences severe, persisting emotional distress, such as panic attacks, severe generalized anxiety, or insomnia following an Experimental Session, the site physician may prescribe a benzodiazepine (specifically, lorazepam) and/or sleep aid (e.g., zolpidem). This medication will be captured on the Concomitant Medications eCRF. The site physician should not prescribe an SSRI, SNRI, or monoamine oxidase inhibitor (MAOI) in this context, unless it has been determined that the participant will be withdrawn from the study. Residual symptoms will be addressed during the frequent follow-up psychotherapy visits with the therapy team.
- 3. If a participant should become psychotic, arrangements should be made to stabilize them or transfer them to the Emergency Department if hospitalization is necessary. Any participant who is hospitalized after a severe psychological reaction will be suspended from the protocol until after recovery or stabilization, at which time the investigator and/or site physician will carefully evaluate the participant's emotional status.

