#### 11.0 Concomitant Medications

## 11.1 Tapering Instructions

The site physician will record concomitant medications during Screening. If the prospective participant is being treated with psychiatric medications at enrollment, the prospective participant will be encouraged to discuss medication tapering with their outside treating physician, if any, and will be required to give the site physician permission to do so as well. The medications will then be tapered in an appropriate fashion to avoid withdrawal effects and discontinued at least five half-lives plus one additional week for stabilization before the first Experimental Session to avoid the possibility of any interaction. Additionally, participants who are taking prohibited opiates will be cross-tapered to an allowable opiate (hydrocodone, morphine, and codeine) under the care of their prescribing physician.

The site physician will consult the prescribing physician to initiate medication tapering for participants, as they must refrain from taking psychiatric medications throughout the study, with some exceptions (see Section 11.2 Allowable Concomitant Medications). The prescribing physician's opinion about medication discontinuation will documented either in writing from the prescribing physician, or in writing by the site physician documenting phone contact with the prescribing physician. Tapering will follow a time course appropriate for the medication based on its half-life, with the first Experimental Session scheduled to occur after complete washout (five half-lives plus at least 1 week for stabilization). If the health of the participant worsens after tapering, the participant will be withdrawn from the study and will be treated according to standard clinical practice. This will be recorded in the eCRF.

The therapy team will request information about any changes in medication at each contact. The site physician will be responsible for reviewing and confirming all medications collected during the study.

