#### 11.3 Prohibited Medications

To be enrolled in the study participants must:

- Refrain from the use of any psychoactive medication not approved by the research team from Baseline through Study Termination (with the exception of gabapentin or certain opiates for pain control).
- Be willing to comply with all medication requirements per protocol. Medications will only be discontinued after enrollment per clinical judgment of the site physician in consultation with the prescribing physician.
- Agree that, for 1 week preceding each Experimental Session to refrain from:
  - o Taking any specified herbal supplement (except with prior approval of the research team).
  - Taking any nonprescription medications (with the exception of non-steroidal anti-inflammatory medications or acetaminophen) unless with prior approval of the research team.
  - o Taking any prescription medications (with the exception of birth control pills, thyroid hormones, or other medications approved by the research team).

The research team should only approve medications that clearly would not be expected to have any interactions with MDMA, including, but not limited to, any drugs with sympathomimetic

activity or activity on the serotonin or other monoamine systems, and any other drugs that would be contraindicated with or have any interaction with monoamine oxidase inhibitors (MAOIs).

The following medications are prohibited as they would present potential confounds for interpretation of the data collected from this study as they have notable serotonergic effects or are under potential or available treatments for PTSD:

Use of Marijuana, St. John's Wort, and other herbs and medicines with notable serotonergic effects are prohibited from Baseline to Study Termination. Any investigational treatments under study for PTSD treatment are prohibited from use concurrent with this study.

Diphenhydramine is excluded from this study unless prior approval is granted by the site physician.

If an SSRI, SNRI, or other antidepressant is used between Experimental Session 1 (Visit 4) and Study Termination (Visit 15), the participant will be withdrawn from treatment and continue in follow-up.

Opiates other than hydrocodone, morphine, and codeine are prohibited from Enrollment Confirmation to Study Termination. Participants taking prohibited opiates will be cross-tapered to an allowable opiate during the Preparatory Period.

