7.0 Sample Size and Power Considerations

MP18 is a one-arm interventional study. Thus, no power nor sample size calculations were required.

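### The protocol disagrees on whether a dosed participant who worsens or is given an antidepressant by the site leaves the study or only the treatment, so collection of the Visit 14 outcome can depend on the section applied

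*Protocol*

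**What the plan says.** Five protocol sections bear on a dosed participant who deteriorates or starts an antidepressant.

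- **9.2.2.2**, on severe and lasting distress after a session: the site physician should not prescribe an SSRI, SNRI or MAOI "unless it has been determined that the participant will be withdrawn from the study".
- **11.1**: "If the health of the participant worsens after tapering, the participant will be withdrawn from the study". No end date is given.
- **11.3**, on antidepressant use between Session 1 and Study Termination: "the participant will be withdrawn from treatment and continue in follow-up". (This section labels Session 1 as Visit 4; elsewhere it is Visit 5.)
- **4.3.4**, on someone who comes to meet an exclusion criterion that affects safety, including a need for prohibited medication: "the participant will discontinue treatment in Experimental Sessions but remain in the study for the associated Integrative Sessions". Rater visits of those who stop treatment but stay in keep to the planned timetable.
- **7.1.3**, among the allowances for COVID-19 or another emergency: "Use of prohibited medications and/or cannabis or initiation of new therapy for participants with significant study delays", with review and a re-taper before treatment resumes.

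Protocol 8.4 says the sponsor will monitor data to "ensure complete data collection for all participants, including those who discontinue treatment". SAP 8.2 and 8.7.1 leave CAPS-5 data obtained after treatment discontinuation out of the primary de jure model. SAP 8.2 places them in a supportive de facto analysis.

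**The concern.** A site-prescribed antidepressant after Session 1 falls under both 9.2.2.2 and 11.3. One makes departure from the study the condition for prescribing; the other keeps the participant in follow-up. Worsening without an antidepressant meets the same split between 11.1, read literally, and 4.3.4. Two sites could treat like participants differently, and both could cite the protocol.

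What is at stake is outcome data that go missing for a reason linked to outcome. The participants concerned are likely to be doing badly, the design has no control arm to offset selective loss, and Protocol 13.1.1.1 treats missing CAPS-5 data as missing at random. A lost Visit 14 also runs against the aim stated in 8.4.

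**Working it through.** There is no planned figure to reproduce: the SAP states that "no power nor sample size calculations were required". The check therefore asks two things of each route. Is a Visit 14 CAPS-5 collected? Does it enter the primary de jure model?

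| Route | Visit 14 CAPS-5 collected? | In the primary model? |
|---|---|---|
| Out of the study (9.2.2.2; 11.1 read literally) | Not assured; depends on how 4.3.4 is applied | No, if not collected |
| Out of treatment, followed (11.3, 4.3.4), before Session 2 | Yes, under 4.3.4 | No; SAP 8.2 and 8.7.1 exclude it |
| Out of treatment, followed, after Session 2 | Yes, under 4.3.4 | Undefined; both doses have been given |
| Emergency exception (7.1.3), sessions resumed | Yes | Yes, with the prohibited medication taken in between |

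**Before Session 2.** Rows one and two give the same result in the primary model at Visit 14. They differ only in the de facto analysis.

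**After Session 2.** No session is left to discontinue, and neither document says whether withdrawal from treatment under 11.3 is *treatment discontinuation* under SAP 8.7.1. Protocol 13.1.1.1 has no exclusion rule for CAPS-5; 13.1.1.2 states one for SDS only. Visit 14 can thus be included, excluded or never obtained.

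Length of that period, from the windows in Protocol Table 1 (Visit 5 to Visit 10: 21 to 35 days; Visit 10 to Visit 14: 42 to 70 days):

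- share = (Visit 10 to 14) / (Visit 5 to 10 + Visit 10 to 14)
- lowest: 42 / (35 + 42) = 54.5%
- highest: 70 / (21 + 70) = 76.9%
- at 28 and 56 days: 56 / 84 = 66.7%

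**Timing within the followed route.** Section 4.3.4 keeps the planned rater timetable. Section 7.4.2 asks for a final CAPS-5 at once when treatment is stopped. So even where follow-up is agreed, the date of the last CAPS-5 is unclear.

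**Illustrative size.** Inputs: 40 participants ("The study will be conducted in up to 40 participants in multiple countries in Europe"); early termination of up to 5% (SAP 8.2); dropout of 8 of 107 in earlier Phase 2 studies (Protocol 1.2.4).

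- 0.05 × 40 = 2 participants; 8/107 = 7.5%, and 0.075 × 40 = 3 participants
- shift in the Visit 14 mean change = m × d / 40, where m participants differ by d points from the rest
- m = 2, d = 10: 20/40 = 0.5 points; m = 2, d = 20: 40/40 = 1.0 point
- m = 3, d = 10: 30/40 = 0.75 points; m = 3, d = 20: 60/40 = 1.5 points

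The difference d is an assumption. Both rates are all-cause; the documents give none for antidepressant use. The shift takes no account of what the model recovers from Visit 8.

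**The case against.** Much can be said for the plan.

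- **Section 9.2.2.2 sets a condition for prescribing; it is not a consequence of use.** Section 11.3 covers use from any source. The two can be read together where an outside doctor starts the drug. They still collide when the site prescribes.
- **Section 11.1 may concern only the time before dosing.** It sits in the tapering instructions, directly after the sentence placing Session 1 after washout. That reading is natural, but the text sets no such limit.
- **Visit 14 is not necessarily lost.** Section 4.3.4 sorts people removed after dosing into those who stop treatment but stay assessed and those who withdraw consent. A site-led removal without withdrawal of consent could be put in the first group and keep its rater visits. Section 7.4.2 and the optional final CAPS-5 for dropouts give further routes. This stands: the loss is possible, not certain. The protocol never says how a participant removed under 9.2.2.2 or 11.1 is classed.

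A reader might infer that there are three incompatible rules, counting 7.1.3. The documents do not support that. Section 7.1.3 is triggered by an emergency delay and not by worsening, it is recorded as a deviation, and it refers to Section 11.0 for the re-taper. What remains is that 11.3 states its consequence without acknowledging the exception.

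**Conclusion.** The point holds as a conflict between two general rules, plus one emergency exception that 11.3 does not acknowledge. It can decide whether an outcome-related Visit 14 CAPS-5 and SDS are collected.

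A reader might go further and infer that the section applied always decides entry into the primary analysis. Before Session 2 it does not: the choice between leaving the study and leaving treatment changes only the de facto analysis. After Session 2, about 55% to 77% of the Visit 5 to Visit 14 interval, the status of Visit 14 is undefined, and there the primary analysis can be affected.

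The size is modest: about 0.5 to 1.5 CAPS-5 points if 2 to 3 of 40 participants are affected and differ by 10 to 20 points. This is an illustration and not an estimate of bias. The difference has no source in the documents, and antidepressant-related cases would be only part of all-cause early termination. Nothing here says which clinical rule is right.

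**What to change.** In the protocol:

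- Reconcile 9.2.2.2, 11.1, 11.3 and 4.3.4, and refer from 11.3 to 7.1.3. The clinical consequence is for the sponsor to decide.
- State the period to which the sentence on worsening in 11.1 applies.
- Whatever consequence is chosen, state that the planned independent-rater assessments continue through Visit 14 for every dosed participant unless consent is withdrawn. This concerns data collection only.
- Reconcile 7.4.2 with 4.3.4 on when the last CAPS-5 is taken, and correct the visit number given for Session 1 in 11.3.

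In the SAP:

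- Define whether antidepressant use or withdrawal after Session 2 is treatment discontinuation for the de jure analysis.
- Flag participants who resume under 7.1.3 after prohibited medication, and run a sensitivity analysis on them.

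The cost is wording in a few protocol sections, a short SAP definition and one sensitivity analysis. The rater visits are already scheduled, so no new assessment is needed.

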#### 9.2.3 Low Level Risks

Low Level Risk does not indicate the likelihood the event will occur but indicates per the RACT assessment that no new or complex procedures are needed to ensure screening is adequate to eliminate or manage the risk in the patient population.

## 9.2.3.1 Thermoregulatory Risks and Mitigation

MDMA administered in a controlled setting produces only a slight increase in body temperature [114]. Ambient temperature does not enhance or attenuate this slight elevation in humans. In data gathered from sponsor-supported Phase 2 and Phase 3 studies, it was found that compared to placebo, a higher percentage of participants receiving MDMA had peak body temperatures greater than 1 degree Celsius (°C) above baseline. However, there was no strong relationship between dose of MDMA and peak body temperature or between MDMA dose and elevation above threshold of 1°C above baseline.

Ambient temperature should be kept at a comfortable level during Experimental Sessions. If a participant's temperature rises more than 1° C or the participant states that they feel hot, attempts should be made to decrease body temperature and increase comfort by removing blankets and layers of clothing, decreasing the ambient temperature, and, if necessary, directing a fan toward the participant. If at any time the temperature rises more than 1.5° C above baseline despite these efforts, the site physician should be consulted for further evaluation and treatment.

